Appendix I

Important Protocol Deviations

	Category of Protocol Deviation	Description of Protocol Deviation	Deviation Code	Protocol Section	Variable [dataset]	Proposed check / comment
Inclusion criteria: For the subject to be eligible for inclusion, each criterion must be checked 'YES':						
Criterion1: Signed written informed consent.	Eligibility and Entry Criteria	Subject did not meet inclusion criterion 1 (signed inform consent form).	PDEV01	Section 5.3.1	DM. RFICDTC	list if DM. RFICDTC is missing or if DM.RFICDTC<Earliest date of SV.SVSTDTC. Medical Review Required.
Criterion2: Male or female subjects aged >=18 years.	Eligibility and Entry Criteria	Subject did not meet inclusion criterion 2 (age >= 18 years).	PDEV02	Section 5.3.1	DM.AGE	List if DM.AGE<18.

	Category of Protocol Deviation	Description of Protocol Deviation	Deviation Code	Protocol Section	Variable [dataset]	Proposed check / comment
Criterion3: Histologically or cytologically proven metastatic or locally advanced solid tumor or related prior anti-cancer therapy.	Eligibility and Entry Criteria	Subject did not meet inclusion criterion 3 (histologically or cytologically proven metastatic or locally advanced solid tumor or prior anti-cancer therapy for metastatic or locally advanced disease).	PDEV03	Section 5.3.1	XX.XXDTC where XXTESTCD='TBP ALL'; SUPPXX.QNAM(F RESHDTC, FRESHTB), QVAL; CM.CMTRT, CMINDC	
Medical review required or programming.
 
List if subject did not meet all of the following requirements (depending on cohort):
 
A. Tumor tissue is available - 1) there is at least one record in XX (XX.XXDTC ne missing where XXTESTCD='TBPALL' and XXCAT='TUMOR BIOPSY OR BLOCK') for all cohorts or at least one record (missing < XX.XXDTC < TRTSDT where XXTESTCD='TBPALL' and XXCAT='UNSCHEDULED TUMOR BIOPSY OR BLOCK') for expansion subjects ; or 2) there is at least one records in SUPPXX (SUPPXX.QVAL='Y' where QNAM= 'FRESHTB') for all cohorts;
 
B. At least one prior anti-cancer therapy for NSCLC and ACC subjects - 1) there is at least one record in CM where CMCAT='PRIOR ANTI-CANCER TREATMENT' and CMSCAT='DRUG THERAPY' and CMTRT ne missing and CMINDC=('METASTATIC', 'LOCALLY ADVANCED', 'PALLIATIVE') for subjects where ACTARMCD=(MSB_EXP_NSCLC, MSB_EXP_ACC);
 
C. No prior anti-cancer therapy for first line NSCLC subjects: - 1) there is NO record in CM where CMCAT='PRIOR ANTI-CANCER TREATMENT' and CMSCAT='DRUG THERAPY' and CMTRT ne missing and CMINDC= ('METASTATIC', 'LOCALLY ADVANCED', 'PALLIATIVE') for subjects where ACTARMCD=(MSB_EXP_FLNSCLC).

	Category of Protocol Deviation	Description of Protocol Deviation	Deviation Code	Protocol Section	Variable [dataset]	Proposed check / comment
Criterion5: Disease must be measurable at least 1 dimension except for CRPC or MBC (dose escalation).	Eligibility and Entry Criteria	Subject did not meet inclusion criterion 5 (measurable disease at least one dimension except for CRPC and escalation MBC subjects).	PDEV04	Section 5.3.1	TR.TRORRES, TRTESTCD; SUPPTR.QNAM, QVAL.	list if TR.TRORRES is missing or not assessable where TRTESTCD=' SUMDIAM' and TRCAT='RECIST' and SUPPTR.QVAL='SCREENING' where QNAM='ASMNTVIS'. Do not check this for subjects where SUPPDM.QVAL = ' CASTRATE-RESISTANT PROSTATE CANCER' where QNAM='COHORT' or SUPPDM.QVAL=' DOSE ESCALATION AND DLT/MTD COHORTS' where QNAM='COHORT' and MHLOC in ('NIPPLE' 'CENTRAL PORTION OF BREAST' 'UPPER-INNER QUADRANT OF BREAST (UIQ)' 'LOWER-INNER QUADRANT OF BREAST (LIQ)' 'UPPER-OUTER QUADRANT OF BREAST (UOQ)' 'LOWER-OUTER QUADRANT OF BREAST (LOQ)' 'AXILLARY TAIL OF BREAST' 'OVERLAPPING LESION OF BREAST 'BREAST, NOS')
Criterion9: Effective contraception for both male and female subjects if the risk of conception exists.	Eligibility and Entry Criteria	Subject did not meet inclusion criterion 9 (effective contraception).	PDEV05	Section 5.3.1		Medical review required
Exclusion criteria: For the subject to be eligible for inclusion, each criterion must be checked 'NO':						
1. Concurrent treatment with a non-permitted drug.	Eligibility and Entry Criteria	Subject met exclusion criterion 1 (non-permitted drug).	PDEV06	Section 5.3.2		Medical review required

	Category of Protocol Deviation	Description of Protocol Deviation	Deviation Code	Protocol Section	Variable [dataset]	Proposed check / comment
2. Prior therapy with any antibody/drug targeting T cell co-regulatory proteins.	Eligibility and Entry Criteria	Subject met exclusion criterion 2 (prior therapy with any antibody/drug targeting T cell co-regulatory proteins).	PDEV07	Section 5.3.2		Medical review required
3. Concurrent anticancer treatment, major surgery, concurrent systemic therapy with steroids or other immunosuppressive agents, or use of any investigational drug within 28 days before the start of trial treatment.	Eligibility and Entry Criteria	Subject met exclusion criterion 3 (concurrent anticancer therapy or surgery, concurrent systemic therapy with steroids or other),	PDEV08	Section 5.3.2		Medical review required
4. Previous malignant disease other than the target malignancy to be investigated in this trial within the last 5 years with the exception of basal or squamous cell carcinoma of the skin or cervical carcinoma in situ	Eligibility and Entry Criteria	Subject met exclusion criterion 4 (previous malignant disease other than the target malignancy to be investigated in this trial within the last 5 years).	PDEV09	Section 5.3.2		Medical review required
12. Pregnancy or lactation period.	Eligibility and Entry Criteria	Subject met exclusion criterion 12 (pregnancy or lactation period).	PDEV10	Section 5.3.2	PREG.PRRLTCD	Medical review required.

	Category of Protocol Deviation	Description of Protocol Deviation	Deviation Code	Protocol Section	Variable [dataset]	Proposed check / comment
Non-permitted concomitant medication during the study	Concomitant Medication Criteria	Subject took prohibited medication during the study.	PDEV11	Section 6.5.2	CMED.CMTERM	Medical review required
Subjects that developed withdrawal criteria whilst on the study but were not withdrawn;	Other Criteria	Subject became pregnant, but continued on the study.	PDEV12	Section 5.5.2	LB.LBORRES, BTESTCD; DS.DSSTDTC, DSSCATE;	Medical review required.
Subjects that developed withdrawal criteria whilst on the study but were not withdrawn;	Other Criteria	Subjects had ECOG>=3, did not resolved to <=2 by day 14 of next cycle, and continued on the study.	PDEV13	Section 5.1.7.2 and 5.5.2	XP.XPORRES, XPDY; DS.DSSTDTC, DSSCATE;	Medical review required.
Subjects that developed withdrawal criteria whilst on the study but were not withdrawn;	Other Criteria	Subject developed grade 4 AE, but continued on the study.	PDEV14	Section 5.1.7.2 and 5.5.2	ADAE.ATOXGRN, TRTEMFL, AREL; SDTM.AE.AEACNOT H; SUPPAE.QVAL, QNAM	List if TOXGRN=4 and AREL='Related' and TRTEMFL='Y' and (SUPPAE.QVAL^='Drug Withdrawn' where QNAM in (ACNMSB, ACNMSB3) and SDTM.AEACNOTH^='LED TO STUDY TERMINATION')
Subjects that developed withdrawal criteria whilst on the study but were not withdrawn;	Other Criteria	Subject developed grade 3 AE, but continued on the study.	PDEV15	Section 5.1.7.2 and 5.5.2	ADAE.ASEVN, TRTEMFL, AEDECOD, AEDUR. DS.DSSTDTC, DSSCATE;	Medical review required.

	Category of Protocol Deviation	Description of Protocol Deviation	Deviation Code	Protocol Section	Variable [dataset]	Proposed check / comment
Subjects overdosed (>=110% of assigned dose)	IP Compliance	Subject was overdosed.	PDEV16	Medical defined.	ADEXSUM.AVAL where PARAMACD='RDOSINT' or 'TRTCMP'	list if individual or cumulative relative dose intensity >=110
Deviation from GCP	Other Criteria	GCP deviation		Section 3.7		Medical review required.
NA	Other Criteria	Other protocol deviation	PDEV99	Medical defined		Medical review required.

Appendix II Description of the Case Review for Assessment of Immune-Related AEs and Definition of Infusion Related Reactions

In order to thoroughly and consistently analyze potential immune-mediated adverse events (AEs), a two-level approach is proposed including:

1. A MedDRA Preferred Term (PT) query is proposed for each event category (i.e., immune-mediated rash, colitis, pneumonitis, hepatitis, nephritis and renal dysfunction, endocrinopathies and other immune-mediated adverse reactions).
2. AEs identified by the MedDRA PT queries will then be medically reviewed using predefined case definitions for immune-mediated adverse reactions.

Level 1:

To identify potentially immune-mediated AEs, the MedDRA PT queries will be used to search for AEs of interest in the clinical database. The proposed event categories such as:

Immune-mediated rash, Immune-mediated colitis, Immune-mediated pneumonitis, Immune-mediated hepatitis, Immune-mediated nephritis and renal dysfunction, Immune-mediated endocrinopathies (Thyroid disorders: Hypothyroidism, Hyperthyroidism, and Thyroiditis), Immune-mediated endocrinopathies (Adrenal insufficiency, Immune-mediated endocrinopathies (Type 1 Diabetes Mellitus), Immune-mediated endocrinopathies (Pituitary dysfunction), Immune-mediated endocrinopathies (Hypogonadism), Other immune-mediated adverse events. Further details e.g. MedDRA PT queries are regularly updated based on the current MedDRA version.

In order to standardize the MedDRA PT queries as much as possible, High Level Terms (HLT) and Standardized MedDRA Queries (SMQ) were used whenever a choice, that was considered reflective of the events of interest, was available.

Level 2:

In a second level (medical review), the potential immune-mediated AEs identified from the search performed at Level 1, will be reviewed by qualified medical personnel to determine whether the AE meets the criteria (case definition) for an immune-mediated adverse reaction based on the following algorithm:

Table 15 Algorithm for immune-related adverse reactions

Criteria	Description
Onset	AE onset after 1st avelumab administration until up to 90 days after last dose
Duration	AE does not spontaneously resolve (i.e., without corticosteroids/ immunosuppressant treatment) within 7 days after onset
Immunosuppressive therapy	AE treated with corticosteroid or other immunosuppressant therapy. For endocrinopathies only: AE required hormone replacement* and /or (corticosteroid or other immunosuppressive therapy)

Etiology	No other clear etiology or Histopathology/biopsy consistent with immune-mediated event
All criteria listed in the left column need to be fulfilled for an event to meet the case definition of immune-mediated reaction.	
*Hormone replacement will be evaluated for specific endocrinopathy disorders only as follows: 
 • Thyroid disorders (HLT): Thyroid therapy (ATC codes (H03A, H03B)) • Diabetes mellitus (including hyperglycemia): Insulin (ATC code A10A) 	

Infusion related reactions are identified based on a list of MedDRA PTs and criteria on the timely relationship according to Table 16.

Table 16 Criteria for infusion related reactions

Infusion related reactions	
Reactions - Considered when onset is on the day of avelumab infusion (during or after the infusion) or the day after the avelumab infusion (irrespective of resolution date):
 
 • Infusion related reaction • Drug hypersensitivity • Anaphylactic reaction • Hypersensitivity • Type 1 hypersensitivity 
Signs and Symptoms - occurring on the day of avelumab infusion (during or after the infusion) and resolved with end date within 2 days after onset
 
 • Pyrexia • Chills • Flushing • Hypotension • Dyspnea • Wheezing • Back pain • Abdominal pain • Urticaria
----------------------------	---

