5.3 Selection of Trial Population

5.3.1 Inclusion Criteria

For inclusion in the trial, all of the following inclusion criteria must be fulfilled:

Inclusion criteria for dose escalation, including the 10 mg/kg once weekly cohort:

1. Signed written informed consent.
2. Male or female subjects aged ≥ 18 years.
3. Histologically or cytologically proven metastatic or locally advanced solid tumors, for which no standard therapy exists or standard therapy has failed. Availability of tumor archival material or fresh biopsies is optional for subjects in dose escalation.
4. ECOG performance status of 0 to 1 at trial entry and an estimated life expectancy of at least 3 months.
5. Disease must be measurable with at least 1 unidimensional measurable lesion by RECIST 1.1, except for subjects with metastatic CRPC or MBC who may be enrolled with objective evidence of disease without a measureable lesion.
6. Adequate hematological function defined by white blood cell (WBC) count $\geq 3 \times 10^9/L$ with absolute neutrophil count (ANC) $\geq 1.5 \times 10^9/L$, lymphocyte count $\geq 0.5 \times 10^9/L$, platelet count $\geq 100 \times 10^9/L$, and hemoglobin ≥ 9 g/dL (may have been transfused). For subjects with

gastric cancer only, the acceptable parameters for WBC, ANC, and lymphocytes are as follows: $WBC \geq 2 \times 10^9/L$, $ANC \geq 1.0 \times 10^9/L$, and lymphocyte count $\geq 0.5 \times 10^9/L$.

- Adequate hepatic function defined by a total bilirubin level $\leq 1.5 \times$ the upper limit of normal range (ULN), an AST level $\leq 2.5 \times$ ULN, and an ALT level $\leq 2.5 \times$ ULN or, for subjects with documented metastatic disease to the liver, AST and ALT levels $\leq 5 \times$ ULN.
- Adequate renal function defined by an estimated creatinine clearance > 50 mL/min according to the Cockcroft-Gault formula.

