- Highly** effective contraception (that is, methods with a failure rate of less than 1% per year) for both male and female subjects if the risk of conception exists (Note: The effects of the study treatment on the developing human fetus are unknown; thus, women of childbearing potential and men must agree to use highly effective contraception, defined in [Appendix III](#) or as stipulated in national or local guidelines. **Highly** effective contraception must be used 28 days prior to first study treatment administration, for the duration of study treatment, and at least for 60 days after stopping study treatment. Should a woman become pregnant or suspect she is pregnant while she or her partner is participating in this study, the treating physician should be informed immediately.)

Inclusion criteria for expansion phase:

- Signed written informed consent.
- Male or female subjects aged ≥ 18 years.
- Subjects must have relapsed, refractory, or progressive disease following last line of treatment (with the exception of the NSCLC first-line and gastric and GEJ cancer primary cohorts, which do not require progression). Availability of tumor archival material or fresh biopsies (excluding bone biopsies) is mandatory for eligibility in the expansion cohorts. For subjects in the MBC cohort, the biopsy or surgical specimen must have been collected within 90 days prior to the first IMP administration. Specifically, the following will be required:

Primary expansion cohorts

- NSCLC post platinum doublet:** Histologically or cytologically confirmed stage IIIB or stage IV NSCLC that has progressed after 1 line of platinum-containing doublet chemotherapy. Subjects should have received only 1 line of platinum-containing treatment for metastatic disease (i.e., adjuvant treatment with a platinum-containing regimen is not sufficient for eligibility because not received in the context of a metastatic disease). Subjects in the NSCLC cohort will only be enrolled in the USA.
- NSCLC first line:** Stage IV (per 7th International Association for the Study of Lung Cancer [IASLC] classification) or recurrent NSCLC that is histologically proven. Subjects must not have received treatment for their metastatic or recurrent disease. No activating EGFR mutation nor ALK translocation / re-arrangement (non-squamous cell histologies require testing if status is unknown).

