9.2 Subject Information and Informed Consent

An unconditional prerequisite for a subject's participation in the trial is his / her written informed consent. The subject's written informed consent to participate in the trial must be given before any trial-related activities are carried out. A separate specific [REDACTED] ICF will be provided to subjects who are willing to participate in this optional procedure, which refers to the extraction and analysis of DNA from blood and / or tumor biopsy in order to better understand how [REDACTED]) may affect the efficacy of avelumab.

Adequate information must therefore be given to the subject by the investigator before informed consent is obtained (a person designated by the investigator may give the information, if permitted by local regulations). A subject information sheet in the local language and prepared in accordance with the Note for Guidance on Good Clinical Practice (ICH Topic E6, 1996) will be provided by the Sponsor for the purpose of obtaining informed consent. In addition to providing this written information to a potential subject, the investigator or his/her designate will inform the subject verbally of all pertinent aspects of the trial. The language used in doing so must be chosen so that the information can be fully and readily understood by lay persons.

Depending on national regulations, a person other than the investigator may inform the subject and sign the ICF, as above.

Where the information is provided by the investigator, the ICF must be signed and personally dated by the subject and the investigator.

The signed and dated declaration of informed consent will remain at the investigator's site, and must be safely archived by the investigator so that the forms can be retrieved at any time for monitoring, auditing and inspection purposes. A copy of the signed and dated information and ICF should be provided to the subject prior to participation.

Whenever important new information becomes available that may be relevant to the subject's consent, the written subject information sheet and any other written information provided to subjects will be revised by the Sponsor or designee and be submitted again to the IEC / IRB for review and favorable opinion. The agreed, revised information will be provided to each subject in the trial for signing and dating. The investigator will explain the changes to the previous version.

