20.1 Programmed Major Protocol Deviations

	Category of Protocol Deviation	Description of Protocol Deviation	Deviation Code	Protocol Section	Variable [dataset]	Proposed check / comment
Inclusion criteria: For the subject to be eligible for inclusion, each criterion must be checked 'YES':						
Criterion1: Signed written informed consent.	Eligibility and Entry Criteria	Subject did not meet inclusion criterion 1 (signed inform consent form).	PDEV01	Section 5.3.1	DM.RFICDTC	list if DM.RFICDTC is missing or if DM.RFICDTC<Earliest date of SV.SVSTDTC. Medical Review Required.
Criterion2: Male or female subjects aged >=18 years.	Eligibility and Entry Criteria	Subject did not meet inclusion criterion 2 (age >= 18 years).	PDEV02	Section 5.3.1	DM.AGE	List if DM.AGE<18.
Criterion3: Histologically or cytologically proven metastatic or locally advanced solid tumor or related prior anti-cancer therapy.	Eligibility and Entry Criteria	Subject did not meet inclusion criterion 3 (histologically or cytologically proven metastatic or locally advanced solid tumor).	PDEV03	Section 5.3.1		Medical review required

	Category of Protocol Deviation	Description of Protocol Deviation	Deviation Code	Protocol Section	Variable [dataset]	Proposed check / comment
Criterion5: Disease must be measurable at least 1 dimension except for CRPC or MBC (dose escalation).	Eligibility and Entry Criteria	Subject did not meet inclusion criterion 5 (measurable disease at least one dimension except for CRPC and escalation MBC subjects).	PDEV04	Section 5.3.1	TR.TRORRES, TRTESTCD; SUPPTR.QNAM, QVAL.	list if TR.TRORRES is missing or not assessable where TRTESTCD=' SUMDIAM' and TRCAT='RECIST' and SUPPTR.QVAL='SCREENING' where QNAM='ASMNTVIS'. Do not check this for subjects where SUPPDM.QVAL = ' CASTRATE-RESISTANT PROSTATE CANCER' where QNAM='COHORT' or SUPPDM.QVAL=' DOSE ESCALATION AND DLT/MTD COHORTS' where QNAM='COHORT' and MHLOC in ('NIPPLE' 'CENTRAL PORTION OF BREAST' 'UPPER-INNER QUADRANT OF BREAST (UIQ)' 'LOWER-INNER QUADRANT OF BREAST (LIQ)' 'UPPER-OUTER QUADRANT OF BREAST (UOQ)' 'LOWER-OUTER QUADRANT OF BREAST (LOQ)' 'AXILLARY TAIL OF BREAST' 'OVERLAPPING LESION OF BREAST' 'BREAST, NOS')
Criterion9: Effective contraception for both male and female subjects if the risk of conception exists.	Eligibility and Entry Criteria	Subject did not meet inclusion criterion 9 (effective contraception).	PDEV05	Section 5.3.1		Medical review required

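### In both SAPs the programmed consent check (PDEV01) compares the dates the wrong way round, so it lists compliant subjects and cannot detect late consent

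*SAP*

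**What the plan says.** **Consent check.** PDEV01 appears in section 20.1 of the dose-escalation SAP and in Appendix I of the expansion SAP. The dose-escalation SAP instructs the programmer to "list if DM.RFICDTC is missing or if DM.RFICDTC<Earliest date of SV.SVSTDTC"; the expansion SAP has the same condition, "if DM.RFICDTC<Earliest date of SV.SVSTDTC". Each cell then asks for medical review. A listed record is described as "Subject did not meet inclusion criterion 1 (signed inform consent form").

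**Protocol rule.** Protocol 9.2 states that written consent "must be given before any trial-related activities are carried out". Section 7.1 requires consent before trial assessments that fall outside routine care, and section 7.1.1 places it before trial investigations at screening.

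**How deviations are found and reported.** Section 12.2.2 of each SAP lets deviations be identified by medical review or by programming, and puts both kinds into the analysis datasets. The dose-escalation SAP reports them in a data listing. The expansion SAP reports them in a table and a listing.

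**Measurable-disease check.** PDEV04 in the dose-escalation SAP describes its exemption as "except for CRPC and escalation MBC subjects". Protocol 5.3.1, dose-escalation criterion 5, requires a measurable lesion "except for subjects with metastatic CRPC or MBC who may be enrolled with objective evidence of disease without a measureable lesion".

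**The concern.** Consent dated before the first visit is what the protocol asks for. A consent date after the first visit is what a timing check should bring forward. PDEV01 does the opposite for both orders.

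Run as written, it would put forward every subject who signed before the day of the first recorded visit, and no subject who signed after it. Section 12.2.2 of each SAP says that dosing a subject who does not meet the inclusion criteria must be reported in the clinical report, and consent is the first criterion. At stake is whether the deviation output can be relied on for consent timing.

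**Working it through.** No figure in the plan is involved, so the check is a comparison of the written condition with the protocol rule. Let C be the consent date (DM.RFICDTC) and V the earliest visit start date (earliest SV.SVSTDTC). The SAPs do not define these variables. The PDEV01 row ties the first to signed consent, and the second is taken to be the visit start date.

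| Order of dates | Status under Protocol 9.2 | PDEV01 as written (C missing, or C < V) | Sign reversed (C missing, or C > V) |
|---|---|---|---|
| C missing | Consent not shown | Listed: right | Listed: right |
| C before V | Compliant | Listed: wrong | Not listed: right |
| C same day as V | Cannot be judged from dates alone | Not listed: acceptable | Not listed: acceptable |
| C after V | Possible late consent | Not listed: wrong | Listed: right |

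The missing-date part works. The date comparison gives the wrong result for both unequal orders, in both SAPs. Neither document limits how early consent may be given, so no other reading makes C < V a failure of criterion 1. The same sign stands in two separate SAPs, so an error in reading the PDF is an unlikely explanation.

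**Does it reach an analysis?** Section 10 of the dose-escalation SAP defines the screening, DLT, safety and PK sets. Section 10 of the expansion SAP defines the screening, PK, safety, full and efficacy sets, with PD-L1 positive subsets. These rest on signing consent (screening only), dosing, DLT-period treatment, measurable concentrations, measurable disease or PD-L1 status. None uses the order of C and V.

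**PDEV04, dose-escalation SAP.** The code skips two groups:
- subjects whose cohort label is castrate-resistant prostate cancer;
- subjects with the dose-escalation cohort label and a primary site in a list of breast sites.

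The second clause implies that escalation subjects carry the escalation label whatever their tumor. An escalation subject with CRPC would then match neither clause, since no prostate site is listed. Without a measurable lesion that subject is listed, although criterion 5 and the check's own description exempt CRPC.

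**The case against.** The strongest reply is that PDEV01 is one screen within a wider process. Section 12.2.2 of each SAP allows medical review to identify deviations in its own right. Appendix I of the expansion SAP has further rows for GCP deviations and other deviations, both under medical review. The disposition listings in section 12.1 of each SAP show consent date and first dosing date. The PDEV01 cell itself calls for review, so compliant subjects may be cleared before output. All of this stands.

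A reader might therefore infer more than the documents support in four ways:

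- **That late consents could not be recovered.** The documents support only that this programmed check would not find them.
- **That every early consent would end up as a reported deviation.** The review step may remove them.
- **That any visit dated before consent is a violation.** Section 7.1 exempts routine care, and section 7.2.5 accepts a CT or MRI done within 4 weeks before first treatment. Dates in the reversed order are a reason to review a case and do not settle it.
- **That PDEV03 part C in the expansion SAP is wrong too.** That check is headed "No prior anti-cancer therapy for first line NSCLC subjects" and lists drug therapy coded as locally advanced, whereas Protocol 5.3.1 says "Subjects must not have received treatment for their metastatic or recurrent disease". But the intent categories in expansion SAP 14.1 contain no code for recurrent disease, so treatment of a locoregional recurrence could be coded as locally advanced. Removing the code could miss barred treatment, and that row already provides for medical review or programming. It is not a clear error.

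None of these replies explains the direction of the sign in PDEV01.

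**Conclusion.** The date comparison in PDEV01 is reversed in both SAPs. When both dates are present, the programmed check detects no late consent and lists every consent dated before the first recorded visit. It covers all subjects; Protocol 8.1 plans about 1,706 treated subjects, which is the reach of the check and not a count of errors. The number with either date order is not given.

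The consequence is limited to the deviation listing in both SAPs and the important-deviation table in the expansion SAP. It would be wrong to infer an effect on the confirmed response analysis, the safety analyses or the DLT analysis, because no analysis set uses the check. The conclusion rests on reading the two variables as consent date and visit start date.

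The PDEV04 gap is minor. It concerns escalation subjects with metastatic CRPC and no measurable lesion, among at most 60 escalation subjects in the dose-escalation SAP. Whether there were any is not stated. It also assumes that these subjects carry the escalation cohort label, as the breast-site clause implies.

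**What to change.** In section 20.1 of the dose-escalation SAP and Appendix I of the expansion SAP, change PDEV01 so that it flags a subject when DM.RFICDTC is missing or when DM.RFICDTC > the earliest SV.SVSTDTC. Keep the instruction for medical review, since some records dated before consent may be routine care and same-day order cannot be read from dates.

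In PDEV04 of the dose-escalation SAP, add an exemption for escalation subjects with metastatic CRPC, to match criterion 5. A prostate primary site alone would be too broad.

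The cost is one operator in two appendices, one added condition, and a re-run of the deviation output. No new data are needed.
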